2.1.4.2 AEs variables

AE observation period

- Pre-treatment AEs are AEs that developed or worsened or became serious from the signed informed consent date up to first dose of double-blind IMP
- Treatment-emergent AEs are AEs that developed or worsened or became serious during the treatment-emergent AE period.
- Posttreatment AE are AEs that developed or worsened or became serious during the posttreatment period.

All adverse events (including SAEs, AESI and EOSI) will be coded to a lower-level term (LLT), preferred term (PT), high-level term (HLT), high-level group term (HLGT), and associated primary system organ class (SOC) using the version of MedDRA currently in effect at Sanofi at the time of database lock.

The occurrence of AEs (including SAEs, AESI and EOSI) will be recorded from the time of signed informed consent until the end of the study (see [Section 2.1.4](#)) or the resolution/stabilization of all SAE, AESI and EOSI.

AESI

- Pregnancy
- Symptomatic overdose with IMP/NIMP
- Alanine aminotransferase (ALT) increase >3 times upper limit of normal (ULN)

EOSI

- Major adverse cardiovascular events (MACE) [cardiovascular death, myocardial infarction, or stroke] and other specific cardiovascular (CV) events (eg, heart failure requiring hospitalization)
- Severe hypoglycemia
Genital mycotic infections (to include vulvovaginal candidiasis in females and candida balanitis in males)
- Urinary tract infections
- Clinically relevant volume depletion and events related/possibly related to volume depletion
- Diarrhea
- Pancreatitis
- Bone fractures
- Venous thrombotic events, to include deep venous thrombosis and thromboembolism (to include pulmonary embolism)
- Diabetic ketoacidosis

Statistical Analysis Plan**Version: 3**

Lexicon Pharmaceuticals Protocol No. EFC14834

Date of Issue: 10 December 2019

Covance Study ID: 000000150525

- Renal events, to include 50% decline in eGFR, end stage kidney disease, renal death
- Malignancies of special interest (breast, bladder, renal cell, Leydig cell, pancreatic, prostate, and thyroid cancer)
- AE leading to an amputation.

A Clinical Endpoint Committee(s) (CEC) will, in a blinded manner review and adjudicate all deaths, myocardial infarction, stroke, unstable angina requiring hospitalization, and heart failure requiring hospitalization, selected renal events, bone fracture, and diabetic ketoacidosis.

Two independent committees will review safety events that require ongoing monitoring to ensure timing protocol amendments in case a safety signal is identified. These events are: 1) potential cases of drug-induced liver injury (DILI), and 2) cases of amputations. The two committees will review the cases in a treatment-blinded manner and will present their assessment to the DMC.

AESI and EOSI will be identified based on criteria in Table 3.

Table 3 - Criteria for AESI and EOSI

AE Grouping	Criteria
AESI	
Pregnancy	eCRF "Pregnancy"
Symptomatic overdose with IMP/NIMP	"Overdose of IMP" or "Overdose of NIMP" checked and "Symptomatic overdose" checked in eCRF "Overdose"
ALT increase > 3X ULN	eCRF "ALT increase"
EOSI adjudicated	
Cardiovascular Death	Positively adjudicated by CEC: "Cardiovascular" or "Undetermined" as the primary cause of death
Myocardial infarction, Unstable Angina requiring hospitalization	Positively adjudicated by CEC: Yes to the question "Does the event meet the definition of an MI for this study?", or Yes to the question "If event is not an MI, does the event meet the definition of an UA Requiring admission to hospital or emergency room, for this study?"
Stroke	Positively adjudicated by CEC: Yes to the question "Does the event meet the definition of a Stroke for this study?"
Heart failure requiring hospitalization	Positively adjudicated by CEC: Yes to the question "Does the event meet the definition of a Heart Failure Event for this study?"
Bone fractures	Positively adjudicated by CEC: Yes to the question "Did the Fracture occur?"
Diabetic ketoacidosis	Positively adjudicated by CEC: Yes to the question "Does this event meet the criteria to be a DKA event?"

EOSI Renal events where select events adjudicated

Statistical Analysis Plan**Version: 3**

Lexicon Pharmaceuticals Protocol No. EFC14834

Date of Issue: 10 December 2019

Covance Study ID: 000000150525

AE Grouping	Criteria
Sustained ≥50% decrease in eGFR	(1) For ≥50% decrease in eGFR from baseline, (1a) confirmed ≥50% decrease in GFR for ≥30 days with no reversible cause as recorded in eCRF “eGFR decrease”, OR (1b) positively adjudicated by CEC: Yes to the question “Does the subject meet the criteria of CKD progression” for ≥50% decrease in eGFR.
Sustained eGFR <15 mL/min/1.73 m ²	(2) For eGFR <15 mL/min/1.73 m ² , (2a) confirmed eGFR <15 mL/min/1.73 m ² for ≥30 days with no reversible cause as recorded in eCRF “eGFR decrease”, OR (2b) positively adjudicated by CEC: Yes to the question “Does the subject meet the criteria of CKD progression”.
Chronic dialysis	(3) For dialysis, (3a) dialysis lasted for ≥90 days (eg, end date – start date+ 1 ≥90) as recorded in eCRF “Renal Event – Dialysis”, OR (3b) positively adjudicated by CEC: Yes to the question “. Does the subject meet the criteria for ESRD”.
Renal transplant *	(4) “Renal transplant” captured in eCRF “Other procedure form”, where adjudication is not required. PTs of Renal transplant (10038533), Renal and pancreas transplant (10052278), Renal and liver transplant (10052279) based on MedDRA v21.1.
Renal death	(5) Renal death as positively adjudicated by CEC: “Death - Non-Cardiovascular (Renal)” as the primary cause of death
EOSI not adjudicated *	
Severe hypoglycemia	algorithm specified in Section 2.1.4.1 based on eCRF “Hypoglycemic Events”
Genital mycotic infections	PTs in Appendix F
Urinary tract infections	PTs in Appendix F
Clinically relevant volume depletion and events related/possibly related to volume depletion	PTs in Appendix F
Diarrhea	Narrow search on “Noninfectious diarrhoea (SMQ)” [20000218] plus the following PTs (MedDRA v21.1): Gastroenteritis (10017888), Antidiarrhoeal supportive care (10055660), Enteritis (10014866), Enteritis leukopenic (10014877), Enterocolitis (10014893), Enterocolitis haemorrhagic (10014896)
Pancreatitis	PTs in Appendix F
Venous thrombotic events	PTs in Appendix F

Statistical Analysis Plan

Version: 3

Lexicon Pharmaceuticals Protocol No. EFC14834

Date of Issue: 10 December 2019

Covance Study ID: 000000150525

AE Grouping	Criteria
Malignancies of special interest	Breast cancer: Narrow search on "Breast cancer: Narrow search on "Breast neoplasms, malignant and unspecified (SMQ)" [20000149] Prostate cancer: Narrow search on "Prostate neoplasms, malignant and unspecified (SMQ)" [20000152] Leydig-cell cancer: PTs of Leydig cell tumour of the testis (10024407) and Ovarian Sertoli-Leydig cell tumour (10073270) based on MedDRA v21.1 Thyroid cancer: PTs in Appendix F Renal cell cancer: PTs in Appendix F Pancreatic cancer: PTs in Appendix F Bladder cancer: PTs in Appendix F

EOSI AE leading to an amputation

AE leading to an amputation	"AE Correction" as the reason for amputation in eCRF "Other Procedures related to Amputation"
AE potentially leading to an amputation *	PTs in Appendix F

* Search terms will be updated using the MedDRA version currently in effect at Sanofi at the time of database lock for EOSI identified by them.
AE potentially leading to an amputation: not an EOSI per individual protocol; analyzed due to their relevance to lower limb complication and amputations as a requirement from health authorities.

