6.1.6 Follow-up period

Following the last dose of IMP (either as scheduled or prematurely), a post treatment follow-up should be scheduled for all patients 4 weeks (\pm 3 days) after permanent IMP discontinuation.

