10.4.1.4 Events of special interest

An EOSI is a serious or non-serious AE of scientific and medical concern specific to the Sponsor’s product or program, for which ongoing monitoring may be appropriate. Such events may require further investigation in order to characterize and understand them. These events should be reported on the specific e-CRF page (where applicable) and will only qualify for expedited reporting when serious (fulfilling SAE criteria).

The EOSI for this study are:

- Major adverse cardiovascular events (MACE [cardiovascular death, MI, or stroke]) and other specific CV events (eg, heart failure leading to hospitalization)
- Severe hypoglycemia (see [Section 10.6.1](#))
- Genital mycotic infections (to include vulvovaginal candidiasis in females and candidal balanitis in males)
- Urinary tract infections
- Clinically relevant volume depletion and events related/possibly related to volume depletion
- Diarrhea
- Pancreatitis
- Bone fractures
- Venous thrombotic events to include deep venous thrombosis and thromboembolism (to include pulmonary embolism)
- Diabetic ketoacidosis
- Renal events to include 50% decline in eGFR, end stage kidney disease, renal death
- Malignancies of special interest (breast, bladder, renal cell, Leydig cell, pancreatic, prostate, and thyroid carcinoma)
- Adverse event leading to an amputation

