11.4.3.4 Analyses of events of special interest

The number (%) of patients with each EOSI event will be summarized by treatment group. All events reported by the Investigators on the AE forms for special interests will be listed along with the adjudication outcome (if applicable).

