- All treatment-emergent SAEs by primary SOC, HLGT, HLT, and PT, showing the number (%) of patients with at least 1 serious treatment-emergent AE, sorted by the internationally agreed SOC order. The other levels (HLGT, HLT, PT) will be presented in alphabetical order.
- All treatment-emergent SAEs regardless of relationship and related to IMP, by primary SOC, HLGT, HLT, and PT, showing the number (%) of patients with at least 1 treatment-emergent SAE, sorted by the internationally agreed SOC order. The other levels (HLGT, HLT, PT) will be presented in alphabetical order.

Analysis of all treatment-emergent AE(s) leading to treatment discontinuation

- All treatment-emergent adverse events leading to treatment discontinuation, by primary SOC, HLGT, HLT, and PT, showing the number (%) of patients sorted by the internationally agreed SOC order. The other levels (HLGT, HLT, PT) will be presented in alphabetical order.

Analysis of adverse events of special interest

The summaries of AESI will be presented for the 79-week entire treatment period only in the safety population.

Pregnancy and overdose will be included in overall AE summaries if any are reported. ALT increase >3 x ULN is included in laboratory PCSA summary if any.

In addition, the number (%) of patients with an AESI will be summarized by PT and by treatment group during the 79-week entire treatment period only. Corresponding listings will be provided as appropriately.

Analysis of events of special interest

The summaries of EOSI will be presented for the 79-week entire treatment period only in the safety population.

CV events, bone fracture and DKA

For EOSIs that are adjudicated (ie, deaths, myocardial infarction, stroke, and unstable angina requiring hospitalization, heart failure requiring hospitalization, bone fracture, and diabetic ketoacidosis), the number (%) of patients with an EOSI positively adjudicated by CEC will be summarized by treatment group. All EOSIs sent for adjudication and/or reported by the investigators in the specific AE forms will be listed along with the adjudication outcome.

Renal events

For the EOSI renal events where selected events are adjudicated, the number (%) of patients with any renal events identified in [Table 3](#) in [Section 2.1.4.2](#) will be summarized by treatment group.

The following renal events will be listed along with the adjudication outcome if applicable, including events,

- i. recorded in eCRF “GFR decrease”,

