Alkaline Phosphatase	>1.5 ULN	Enzymes activities must be expressed in ULN, not in IU/L. Concept paper on DILI – FDA draft Guidance Oct 2007. Internal DILI WG Oct 2008.
Total Bilirubin	>1.5 ULN >2 ULN	Must be expressed in ULN, not in μ mol/L or mg/L. Categories are cumulative. Concept paper on DILI – FDA draft Guidance Oct 2007. Internal DILI WG Oct 2008.
Conjugated Bilirubin	>35% Total Bilirubin and TBILI>1.5 ULN	Conjugated bilirubin dosed on a case-by-case basis.
ALT and Total Bilirubin	ALT>3 ULN and TBILI>2 ULN	Concept paper on DILI – FDA draft Guidance Oct 2007. Internal DILI WG Oct 2008. To be counted within a same treatment phase, whatever the interval between measurement.

Statistical Analysis Plan

Version: 3

Lexicon Pharmaceuticals Protocol No. EFC14834

Date of Issue: 10 December 2019

Covance Study ID: 000000150525

**CRITERIA for POTENTIALLY CLINICALLY SIGNIFICANT ABNORMALITIES
for phase 2/3 studies (oncology excepted)**

Parameter	PCSA	Comments
CPK	>3 ULN >10 ULN	FDA Feb 2005. Am J Cardiol Apr 2006. Categories are cumulative. First row is mandatory. Rows following one mentioning zero can be deleted.
CLcr (mL/min)	<15 (end stage renal disease)	FDA draft Guidance 2010
(Estimated creatinine clearance based on the Cokcroft-Gault equation)	≥15 - <30 (severe decrease in GFR) ≥30 - < 60 (moderate decrease in GFR) ≥60 - <90 (mild decrease in GFR) ≥ 90 (normal GFR)	Pharmacokinetics in patients with impaired renal function-study design, data analysis, and impact on dosing and labeling
eGFR (mL/min/1.73 m ²)	<15 (end stage renal disease)	FDA draft Guidance 2010
(Estimate of GFR based on an MDRD equation)	≥15 - <30 (severe decrease in GFR) ≥30 - < 60 (moderate decrease in GFR) ≥60 - <90 (mild decrease in GFR) ≥ 90 (normal GFR)	Pharmacokinetics in patients with impaired renal function-study design, data analysis, and impact on dosing and labeling
Creatinine	≥150 µmol/L (Adults) ≥30% change from baseline ≥100% change from baseline	Benichou C, 1994.
Uric Acid		Harrison- Principles of internal Medicine 17 th Ed., 2008.
Hyperuricemia	>408 µmol/L	
Hypouricemia	<120 µmol/L	
Blood Urea Nitrogen	≥17 mmol/L	
Chloride	<80 mmol/L ≥115 mmol/L	
Sodium	≤129 mmol/L ≥160 mmol/L	
Potassium	<3 mmol/L ≥5.5 mmol/L	FDA Feb 2005.
Total Cholesterol	≥7.74 mmol/L	Threshold for therapeutic intervention.
Triglycerides	≥4.6 mmol/L	Threshold for therapeutic intervention.

Statistical Analysis Plan

Version: 3

Lexicon Pharmaceuticals Protocol No. EFC14834

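### SAP Table 3 counts only sustained eGFR declines, so no planned table gives a by-arm count of the protocol's renal event, any 50% fall in eGFR

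*SAP*

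**What the plan says.** Protocol 10.4.1.4 gives the renal EOSI as "Renal events to include 50% decline in eGFR, end stage kidney disease, renal death". It sets no minimum duration and does not exclude reversible causes. Protocol 11.4.3.4 then commits to the analysis: "The number (%) of patients with each EOSI event will be summarized by treatment group".

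The EOSI list in SAP 2.1.4.2 repeats the item without qualification: "Renal events, to include 50% decline in eGFR, end stage kidney disease, renal death". Table 3 of the same section, which sets the working criteria, labels the event as sustained and gives two routes joined by OR:

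- (1a) "confirmed ≥50% decrease in GFR for ≥30 days with no reversible cause as recorded in eCRF", on the eGFR-decrease page;
- (1b) positive CEC adjudication as CKD progression for a decrease of 50% or more. The SAP states no 30-day condition for this route.

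The count follows Table 3. SAP 2.4.5.2 reads "For the EOSI renal events where selected events are adjudicated, the number (%) of patients with any renal events identified in" that table, by treatment group. Entries on the GFR-decrease page are listed with any adjudication outcome. The history table in SAP 1.6 records the renal detail, from version 1, as a clarification for consistency with outcome studies.

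On timing, Protocol 6.1.6 says "a post treatment follow-up should be scheduled for all patients 4 weeks" (±3 days) after permanent discontinuation, and Protocol 10.1.4.1 includes clinical chemistry at that visit.

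**The concern.** The event that is counted is narrower than the event the protocol defines and promises to count. What drops out is the acute, reversible fall. Protocol 4.6 names severe renal events and volume depletion with serious consequence among the identified and potential risks, Protocol 10.4.6 gives acute renal insufficiency its own management chart, and Protocol Appendix D links the drug class to volume depletion.

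The renal EOSI table is where a reader will look for the comparison between arms. Under Table 3 it could show no difference, or no events, while acute 50% falls were more frequent in one arm.

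There is also a lesser timing question: whether a decline first seen at the last on-treatment visit can meet a 30-day rule when the final scheduled sample is taken four weeks later.

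**Working it through.** **1. Definitions side by side.**

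| Source | Condition on a 50% eGFR decline |
|---|---|
| Protocol 10.4.1.4 | none |
| SAP 2.1.4.2, EOSI list | none |
| SAP Table 3, route (1a) | at least 30 days and no reversible cause |
| SAP Table 3, route (1b) | CEC finds CKD progression |

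A reversible fall fails (1a) by its terms. It is unlikely to be called CKD progression under (1b), although the CEC charter that would settle this is not among the documents. The other renal rows of Table 3 (sustained eGFR below 15, chronic dialysis, transplant, renal death) are more advanced outcomes and would not pick it up.

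**2. Does another planned table count it?** The MDRD formula in SAP 2.5.1 makes eGFR proportional to creatinine to the power −1.154. Ignoring the small change in age over the trial:

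- Creatinine ratio for a 50% eGFR fall: 2^(1/1.154) = 1.82, a rise of 82%.
- eGFR fall at a 30% creatinine rise: 1 − 1.3^(−1.154) = 0.26.
- eGFR fall at a 100% creatinine rise: 1 − 2^(−1.154) = 0.55.

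The creatinine criteria for potentially clinically significant abnormalities (PCSA) in SAP Appendix E include a 30% change and "≥100% change from baseline". Every 50% eGFR fall meets the 30% row, but that row mixes it with falls from about 26% upward. The 100% row misses creatinine rises of 82% to 99%. The eGFR criteria in Appendix E are absolute bands. For illustration, a patient falling from 120 to 60 lands in the mild-decrease band. No row counts a decline of 50% or more as such.

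**3. Visit 13 to Visit 14.** The flow chart places these visits at Days 551 and 579. The plan's stated interval reproduces: 579 − 551 = 28 days, or 25 to 31 days with ±3.

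- Elapsed days of at least 30: days 30 and 31 only, so 2 of 7 permitted days.
- Counted inclusively (end − start + 1, as Table 3 does for dialysis): days 29, 30 and 31, so 3 of 7.
- The nominal 28 days fails on either count.
- If each visit moves independently within its flow-chart window (Days 548–555 and 576–582), gaps run from 21 to 34 days. Then 15 of 56 day pairs (27%) reach 30.

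**4. How far the timing issue extends.** Visit 13 is the first scheduled chemistry since Week 65: 551 − 455 = 96 days, and 96/551 = 17% of planned treatment time. This is calendar time between samples, not a share of events. For patients who stay on the visit schedule, a decline first seen at any chemistry visit from Week 4 to Week 65 has a later scheduled sample 42 to 96 days on. Among on-treatment visits, the shortfall is therefore confined to Visit 13.

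**The case against.** The protocol groups the decline with end-stage kidney disease and renal death, which suggests progression rather than acute injury, and SAP 1.6 has disclosed the added renal detail since version 1. That is a fair defence of keeping the sustained definition, and it answers any suggestion of concealment. It does not explain why the protocol and the SAP's own list stay unqualified, and a clarification is not the same as saying that the counted event is narrower.

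A reader might also infer that end-of-treatment declines drop out of the count altogether. The documents do not support this. Route (1b) carries no stated 30-day condition. Protocol 10.4.2 allows observation beyond the last planned visit, and SAP 2.1.4 follows EOSIs to resolution or stabilization. Visit 14 itself can fall on day 30 or 31.

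Nor would acute cases be visible only in a listing. All of them meet the 30% creatinine row, which is summarized by arm. Protocol 10.4.2 gives laboratory abnormalities defined as EOSIs as an example for adverse event recording, subject to the investigator's judgement, and recorded events enter the by-arm tables. Some might be coded to prerenal failure, which SAP Appendix F counts under volume depletion.

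These points limit the consequence. None of them supplies a by-arm count of eGFR declines of 50% or more.

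**Conclusion.** The concern holds in limited form. Table 3 narrows the protocol's renal EOSI, and acute, reversible falls of 50% or more are largely absent from the renal count. They remain elsewhere in the safety output, but only in listed, non-specific or reporting-dependent form. The nearest table row that captures all of them starts at an eGFR fall of about 26%.

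The Visit 13 timing point is secondary: 2 of 7 permitted days, or 3 of 7 counted inclusively, reach the 30-day rule, with other routes to confirmation open.

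The conclusion assumes that the CEC would not usually class a reversible fall as CKD progression. The documents give no expected event rate; numbers are presumed small. This is an inexpensive improvement to safety reporting and does not affect the efficacy analyses.

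**What to change.** - Keep the sustained row of Table 3 as defined, including the 30-day rule, for consistency with outcome studies.
- Add to Table 3 and SAP 2.4.5.2 a by-arm row: any decrease of 50% or more in eGFR from baseline (central laboratory) during the treatment-emergent period, confirmed or not.
- State in SAP 1.6 that Table 3 narrows the protocol EOSI.
- Let the new row carry declines first seen at Visit 13 that are never confirmed. Shortening the persistence rule, for example to 25 days, is not recommended: it would depart from the outcome-study definition, and it could still fail because the visit windows allow a gap of 21 days.

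The cost is SAP wording and one table row from creatinine values already collected, with no new samples. The row will include transient falls and may look slightly less favourable than the sustained count.

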2.1.4.3 Deaths

The deaths observation period are per the observation periods defined above.

- Death on-study: deaths occurring during the on-study observation period
- Death on-treatment: deaths occurring during the treatment-emergent AE period
- Death post-study: deaths occurring after the end of the study.

2.1.4.4 Laboratory safety variables

Clinical laboratory data consists of blood analysis (including hematology, clinical chemistry, amylase, lipase, lipid profile) and urinalysis. Clinical laboratory values will be summarized in both standard international units and conventional units when applicable.

Blood samples for clinical laboratories will be taken at designated visits as specified in protocol (see study flowchart in Appendix H). Clinical laboratory values will be summarized by the following groups:

- Hematology
 - **Red blood cells and platelets:** hemoglobin, hematocrit, red blood cell count, platelet count
 - **White blood cells:** white blood cell count, differential count (neutrophils, lymphocytes, monocytes, basophils, eosinophils)

- Clinical chemistry
 - **Metabolism:** glucose (serum), creatine phosphokinase (CPK)
 - **Electrolytes and minerals:** sodium, potassium, chloride, bicarbonate (ie, carbon dioxide), calcium, phosphorus, magnesium
 - **Renal function:** blood urea nitrogen (BUN), creatinine, uric acid
 - **Liver function:** total protein, albumin, alanine aminotransferase (ALT), aspartate aminotransferase (AST), alkaline phosphatase (ALP), total bilirubin, lactic acid dehydrogenase (LDH)
- Lipid parameters (fasting)
 - Total cholesterol (TC)
 - High density lipoprotein cholesterol (HDL-C)
 - Low density lipoprotein cholesterol (LDL-C) (calculated by Friedwald equation)
 - Non-HDLC (calculated as the difference between TC and HDLC)
 - Triglycerides (TG).
- Pancreatic enzymes: lipase, amylase.
- Blood Markers of Intestinal Transit and Absorption
 - Vitamins: B6, B12, K, E and A
 - Serum folate
 - Ferritin
- Markers of bone and calcium metabolism
 - Calcium,
 - 25-hydroxyvitamin D,
 - 1,25-dihydroxyvitamin D,
 - Phosphorus,
 - Parathyroid hormone (PTH),
 - Markers of bone resorption: N-terminal telopeptide (NTX), beta-C-terminal telopeptide (β -CTX-1),
 - Marker of bone formation: type 1 procollagen N-terminal (P1NP).

Urine samples will be collected at designated visits (see study flowchart in Appendix H) and measured by central laboratory:

- Urine dipstick includes: specific gravity, pH, protein, blood, ketones, bilirubin, urobilinogen, nitrite, and leukocyte esterase
- Urine microscopy includes, but is not limited to: detection of formed cellular elements, casts, bacteria, yeast, parasites, and crystals in centrifuged urine sediment
- Urine markers of bone and calcium metabolism: calcium and phosphorus
- Urine albumin, calcium, glucose and creatinine.

Serum glucose, UGE, calculated UACR and calculated UGCR will be presented as efficacy parameters in [Section 2.4.4](#). For creatinine and calculated eGFR, PCSA summaries will be presented in the safety section while descriptive summaries in the efficacy section.

Technical formulas are described in [Section 2.5.1](#).

2.1.4.5 *Vital signs variables*

Vital signs include: heart rate, systolic and diastolic blood pressure, temperature, and respiratory rate (see study flowchart in Appendix H for designated visits). They will be performed after the patient has been seated for at least 5 minutes. Blood pressure and heart rate will be measured 3 times with at least 1 minute between each measurement. The mean of the 3 measurements will be analyzed for each vital sign variable (Heart rate, SBP, and DBP).

2.1.4.6 *Physical examination*

A complete physical exam will be performed at Visit 1/Screening, Visit 9/Week 26, and Visit 13/Week 79. “Normal”, “Abnormal”, “Not done” as determined by the Investigator will be reported in the e-CRF by body system.

2.1.4.7 *Electrocardiogram variables*

12-lead ECGs will be performed at Visit 1/ Screening, Visit 3/ Randomization, Visit 9/ Week 26, and Visit 13/ Week 79. ECG status of “normal” or “abnormal” will be reported in the eCRF as determined by the Investigator.

2.1.5 *Pharmacokinetic variables*

Pharmacokinetic variables include the concentration of sotagliflozin and its 3-O-glucuronide metabolite in the sotagliflozin group.

2.2 *DISPOSITION OF PATIENTS*

This section describes patient disposition for both patient study status and the patient analysis populations.

Screened patients are defined as all patients who signed the informed consent.

Randomized patients consist of all patients with a signed informed consent form who have had a treatment kit number allocated and recorded in the IRT database, regardless of whether the treatment kit was used or not.

For patient study status, the total number of patients in each of the following categories will be presented in the clinical study report using a flowchart diagram or summary tables:

- Screened patients
- Run in patients: patients who had a run-in record in IRT
- Screen failure patients (including failures during run-in) and reasons for screen failure (see Appendix A for details on the mapping of inclusion and exclusion criteria under the original protocol and Amendment 1)
- Nonrandomized but treated patients
- Randomized patients
- Randomized but not treated patients
- Randomized and treated patients
- Patients who have completed the 26-week double-blind core treatment period (see [Section 2.5.4](#)) as per protocol
- Patients who did not complete the 26-week double-blind core treatment period (see [Section 2.5.4](#)) as per protocol and the reasons for permanent treatment discontinuation
- Patients who have completed the 79-week double-blind entire treatment period as per protocol (double-blind core treatment period and extension treatment period)
- Patients who did not complete the 79-week double-blind entire treatment period as per protocol, and the reasons for permanent treatment discontinuation
- Patients who have completed the study as per protocol
- Patients who did not complete the study as per protocol and the reasons for study discontinuation
- Patients' end of study status (completed, not completed) and corresponding end of entire treatment status (completed, not completed)
- Status at last study contact.

For screened, run-in, screen failure, and nonrandomized but treated patients, percentages will be calculated using the number of screened patients as the denominator. All other categories of patients will be presented by treatment group and the percentages will be calculated using the number of randomized patients within each treatment group as the denominator. Reasons for treatment discontinuation will be supplied in tables giving numbers and percentages by treatment group. Patients prematurely discontinued from treatment and/or study, along with reasons for discontinuation, will also be listed.

A summary of the distribution of patients by country and center will also be provided (overall number of patients screened, run-in, randomized, and treated, as well as number of patients randomized, discontinued from study treatment, and discontinued from study for each treatment group).

Patients treated but not randomized, patients randomized but not treated and patients randomized but not treated as randomized will be identified and described in separate listings. The patients of the third category (randomized and not treated as randomized) will be part of efficacy and safety analyses ([Section 2.3](#)). Patients randomized but not treated will be included in efficacy analysis. Safety data of patients treated but not randomized will be reported separately.

The randomization strata [HbA1c at Screening ($\leq 8.0\%$, $>8.0\%$) and mean SBP (<130 , ≥ 130 mmHg)] assigned by IRT will be summarized. The percentages will be calculated using the number of randomized patients as the denominator. The discrepancy between the strata assigned by IRT and the information reported on eCRF will be listed for all randomized patients.

Kaplan-Meier (KM) plots of the cumulative incidence of double-blind IMP discontinuation due to any reason and due to AE will be provided for the entire 79-week double-blind treatment period separately (see [Section 2.5.4](#)). A listing of these patients, along with the reason for discontinuation treatment, study completion status and the reason for discontinuation study, will be provided.

For ABPM sub-study, the number of patients in each of the following categories will be summarized.

- Patients who consented to ABPM substudy
- Patients not entering ABPM substudy and the reason for not entering
- Patients who randomized and entered ABPM substudy (ie, ABPM substudy population, see [Section 2.3.1.2](#))
- Patients who completed ABPM substudy
- Patients who discontinued ABPM substudy and the reason for discontinuation:
 - Adverse Event
 - Study Terminated by Sponsor
 - At patient's own request
 - Lost to follow-up
 - Poor compliance to Protocol
 - Other
- Patients with good quality (see Appendix C) ABPM measurements at either Visit 7A/Week 12, or Visit 9A/Week 26 or both visits.

For patients who consented but did not enter ABPM substudy, percentages will be calculated using the number of patients consented to substudy as the denominator. All other categories of patients will be presented by treatment group and the percentages will be calculated using the number of patients randomized and entered substudy within each treatment group as the denominator. Reasons for ABPM substudy discontinuation will be supplied in tables giving numbers and percentages by treatment group. Patients prematurely discontinued the substudy, along with reasons for discontinuation, will also be listed. Patients who consented but did not enter ABPM substudy, along with reasons for not entering, will also be presented.

All important deviations including randomization and drug-dispensing irregularities will be summarized in tables giving numbers and percentages of deviations by randomized treatment group.

Additionally, the analysis populations for safety, efficacy, ABPM substudy, and pharmacokinetics defined in [Section 2.3](#) will be summarized in a table by number of patients in the randomized population.

- Efficacy population: intent-to-treat (ITT) population
- Efficacy population for substudy: ABPM substudy population
- Safety population
- PK population.

